Secondary endpoints will be assessed similarly. Steps, calories, and hours using the app tracker will be collected by the device. These will be aggregated to a weekly total or daily average over the week-long period to smooth out day-to-day variation. Analyses will be performed using linear mixed effects models with these weekly total data, separately for each endpoint. Weight loss as recorded by the Bluetooth scale at home will be analyzed similarly, taking the average of assessments over the course of each week as the outcome [recall, the primary endpoint is weight loss measured in clinic at study visits]. Number of exercise sessions will be evaluated, also as a weekly total number of sessions, using generalized linear mixed effects models with the outcome analyzed as a Poisson count. The distribution of each outcome will be assessed and alternative approaches considered as necessary. Quality of Life questionnaires will be assessed at study visits and analyzed using linear mixed effects models to compare between groups. The primary outcome has been pre-specified and no adjustment will be made for comparisons of these secondary outcomes.

An exploratory aim will evaluate adherent vs non-adherent patients – and further the interaction between adherent (vs non-adherent) and randomized group, to assess whether there is a differential response to Phentermine-Topiramate among exercise adherent patients. Adherence will be defined by 80% use during the first 3 months.

Anticipated results and significance:

Our study will demonstrate the importance of combining a consumer-based wearable activity tracker with an Anti-obesity Pharmacotherapy in Obesity.

Potential pitfalls, precautions taken, and alternative strategies:

- a. Feasibility - Given high volume of patients interested in weight loss, we are confident we will recruit sufficient participants for these studies that involve only noninvasive tests and standard of care treatment.
- b. Statistical power has been addressed with appropriate sample sizes to demonstrate a difference in weight change vs. placebo.

References

- 1 Gadde, K. M. *et al.* Effects of low-dose, controlled-release, phentermine plus topiramate combination on weight and associated comorbidities in overweight and obese adults (CONQUER): a randomised, placebo-controlled, phase 3 trial. *Lancet* **377**, 1341-1352, doi:10.1016/s0140-6736(11)60205-5 (2011).

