A computer generated randomization schedule generated by the study statistician's office will be submitted to the Mayo Clinic CCaTS Research Pharmacy. Randomization will be based on guiding pharmacotherapy or placebo. Allocations will be concealed. This study will be blinded until data are transmitted to the statistician for data lock. All subjects will be given a verbal explanation of the study, provided time to read and study the written consent form and its information, given opportunities to ask questions and a copy of the consent form. Participants will be informed of their right to withdraw from the study at any time without prejudice to their clinical management now or in the future. Consent will be sought by one of the medical doctor investigators or the study coordinator, and consent will be documented by the participant's signature on the consent form. Mayo's Institutional Review Board will approve the process and protocol. All the members of multidisciplinary team for weight management (i.e. physicians, coordinators, clinical assistants, registered dietitians will remain blinded).

If unblinding is needed for subject safety the Principal Investigator or a Co-Investigator will contact a research Pharmacist or the research pharmacy manager and provide documentation of reason for study unblinding and the subject will be withdrawn from the study. The study team will document and report the reason for unblinding as required by the Mayo Clinic IRB.

Selection Participants

We plan to study a cohort of 80 patients with obesity ($BMI > 30 \text{ kg/m}^2$). Participants will be recruited from the Mayo Clinic Weight Management and Nutrition Clinic, media advertising, classified ads, and existing databases of patients with obesity, including the phenome registry (Mayo Clinic IRB number [REDACTED]), the Mayo Clinic biobank and the right-10k cohort.

Inclusion criteria

- a) Adults with obesity ($BMI > 30 \text{ Kg/m}^2$); these will be otherwise healthy individuals with no unstable psychiatric disease and controlled comorbidities or other diseases.
- b) Age: 18-75 years.
- c) Gender: Men or women. Women of childbearing potential will have negative pregnancy tests within 48 hours of enrollment.
- d) Women of childbearing potential must agree to use a method of effective contraception during study participation.

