Subjects in the study will be provided with an Apple watch Series 5. The Apple watch will be connected by Bluetooth technology to the subject's personal Apple iPhone. Subjects will be required to use the watch during the study.

Digital Wellness Devices:

Subjects in the study will be provided a wireless scale, automated blood pressure cuff and pulse oximeter. These digital wellness devices will be connected by Bluetooth technology to the subject's personal Apple iPhone.

Subjects will be allowed to keep the wearable activity tracker and the digital wellness devices if they complete the study. Subjects who withdraw from the study or are withdrawn from the study will be asked to return the digital wellness devices. Subjects will also be provided with a backpack to transport the wellness devices.

Virtual Care:

As part of the study subjects will be asked to download the VitalCare (VitalTech Affiliates LLC) application to the subject's personal Apple iPhone from the Apple App Store. This application will allow the study team to conduct the remote study visits. The application will also be used to monitor subject compliance with taking the study medication and to send reminders to the subject to take the study medication. Additionally this application will record the measurements collected by the digital wellness devices given to the subjects as part of the study. The study subjects will not be required to use the digital wellness devices at any set time points, but it will be encouraged. The digital wellness devices will be used at the subject's discretion. Any measurements recorded by the digital wellness devices will only be reviewed by the study team during the subject's study visits, either in person visits or remote visits. Study team will not monitor the use or results of this study until the next scheduled visit or until the participant brings it to our attention.

Medication

Medication Phentermine-Topiramate Extended Release and matching placebo will be provided by Vivus, Inc (California, US). See FDA drug information package.

Pregnancy Testing

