The primary analysis will be conducted under intention to treat (ITT) principles. Since study drug is administered double-blind, all subjects taking at least one dose of study drug will be included in analyses.

Primary endpoint: The primary endpoint is weight at 3 months (12 week visit), compared between groups using Analysis of Covariance (ANCOVA), adjusted for baseline weight. Subjects without follow up (dropouts) will have values imputed using multiple imputation. This approach assumes the distribution of missing data is random after conditioning on observed data in the imputation process. A secondary approach will consider complete case data, though this does not generally adhere to ITT principles.

Weight is recorded longitudinally at several post-baseline timepoints. A secondary analysis will model these longitudinal data using linear mixed effects models, adjusted for baseline weight. Additional adjustment variables will be included based on *a priori* determination by investigators that such variables may be associated with the dropout process. Thus, any dropout is assumed Missing At Random as a function of observed data. Time after randomization will be included as a discrete ordinal variable corresponding to the visit number. The primary comparison is a time by treatment group interaction, so that contrasts of the variables in the model will allow estimation of the treatment effect at each visit.

An interim analysis will be performed after 50% of subjects have completed their 3 month visit. This will allow the study team to review data quality and check assumptions related to the power calculation (including the standard deviation

above). Investigators will remain blinded to group comparisons and while investigators have no intention of stopping the study early (regardless of interim results), the analysis at study completion will be conservatively adjusted using the O'Brien-Fleming boundary (two-sided significance level of 0.0492).

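### A participant unblinded for safety leaves the study, so later weights go unmeasured and an analysis labelled ITT must impute them under missing at random

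*Combined protocol and SAP*

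**What the plan says.** In the protocol's Randomization and Allocation section, an investigator who needs the blind broken for a participant's safety must contact the research pharmacy and document the reason, and then "the subject will be withdrawn from the study". The rule names the study, not the study drug. No section lets a participant stop drug and stay in follow-up, and none describes visits after withdrawal.

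The Digital Wellness Devices section adds: "Subjects who withdraw from the study or are withdrawn from the study will be asked to return the digital wellness devices". Those devices include the wireless scale, so home weights end as well.

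The Statistical Analysis section states: "The primary analysis will be conducted under intention to treat (ITT) principles". It defines the analysis set so that "all subjects taking at least one dose of study drug will be included in analyses". For a missing month-3 weight it says: "Subjects without follow up (dropouts) will have values imputed using multiple imputation", and adds: "This approach assumes the distribution of missing data is random after conditioning on observed data in the imputation process". The alternative is described this way: "A secondary approach will consider complete case data, though this does not generally adhere to ITT principles". The longitudinal mixed model also assumes that dropout is missing at random.

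**The concern.** Under intention to treat, the month-3 weight of someone unblinded for safety is part of the outcome of their assigned arm, whatever they take afterwards. The plan keeps that person in the analysis but stops measuring them, so a protocol rule creates missing data that need not be missing.

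The replacement value rests on an assumption that is weakest for exactly these people. Missing at random says that, given the observed data, a participant who left after a safety event would have weighed what comparable participants who stayed weighed. If those who stayed were still on active drug and the one who left would have been off it, the imputed weight is too favourable to the drug.

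There may also be little to condition on. The list of anthropometric measurements runs from randomization day to visit 5, which is month 3. The flowsheet marks vital signs at week 4 without saying whether weight is among them.

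No planned analysis would reveal a problem. The imputation and the mixed model share the assumption, and the complete-case analysis leaves these participants out.

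**Working it through.** **Inputs from the protocol.** 80 participants randomized 1:1, so 40 per arm; SD 3 kg; differences to detect of 1, 1.5 and 2 kg (Sample size assessment and power calculation); final two-sided level 0.0492 (Statistical Analysis). The 2 kg row is the one that fits a total near 80.

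**Reproducing the plan's own figure.** The table states neither power nor alpha. With 80% power and two-sided 0.05 assumed, the normal formula is n = 2(1.960 + 0.842)² × 3²/Δ². For Δ = 2 this is 2 × 7.85 × 9/4 = 35.3, so 36 per group. The t-test version gives 142.2, 63.8 and 36.3 for 1, 1.5 and 2 kg, which round up to the stated 143, 64 and 37. The table holds, and this point disputes no number in it.

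**Precision at 40 per arm.** SE = 3 × √(2/40) = 0.67 kg. Power for 2 kg at 0.0492 is 84.5% (normal) or 83.6% (t).

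**Overstatement.** Let k be the number of active-arm participants unblinded and withdrawn before month 3, and f the share of the drug effect they would have lost by month 3. If they are imputed at the on-drug mean of their arm:

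overstatement = (k/40) × f × 2 kg

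For k = 1 and f = 1 this is 2/40 = 0.05 kg. The documents give no unblinding rate, so k is shown as a range. k = 8 is 20% of the arm, equal to the plan's largest total dropout scenario, and is included only as an outer edge.

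| k | Overstatement, f = 1 | Overstatement, f = 0.5 | Difference if followed, f = 1 | Overstatement / SE, f = 1 | Power for the followed difference (normal), f = 1 |
|---|---|---|---|---|---|
| 1 | 0.05 kg | 0.025 kg | 1.95 kg | 7% | 82.6% |
| 2 | 0.10 kg | 0.05 kg | 1.90 kg | 15% | 80.7% |
| 4 | 0.20 kg | 0.10 kg | 1.80 kg | 30% | 76.3% |
| 8 | 0.40 kg | 0.20 kg | 1.60 kg | 60% | 66.2% |

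Placebo-arm cases add nothing in this calculation, because a placebo participant has no drug effect to lose. Any imbalance between arms therefore governs how large k may be, not the size per case.

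**Timing.** Unblinding after the month-3 visit leaves the primary endpoint intact and affects only weight and other outcomes at 6, 9 and 12 months. Cases can accumulate there, but the documents give neither a rate nor a planned effect for those times, so no figure is offered.

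**The case against.** The case against giving this weight is substantial, and most of it stands.

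- A reader might infer that unblinded participants are removed from the primary analysis. They are not: anyone dosed stays in and is imputed. Only the secondary complete-case analysis omits them, and the plan itself concedes that analysis's weakness.
- A reader might infer that safety unblinding is known to be more frequent on active drug. That is plausible, given the adverse events listed in the introduction, but no document gives a rate by arm.
- A reader might extend the rule to everyone who stops drug for an adverse event. It covers only cases where the blind must be broken for safety, and a participant can stop without that. The affected group is probably much smaller.
- The imputation model is not specified. Imputing at the on-drug mean is a worst case; weights seen before withdrawal could move the imputed value. A safety event could also change weight in either direction, so the sign of the bias is conditional.
- Home scale use is voluntary and home weight is not the primary endpoint, so those data were never assured.
- Keeping an unblinded participant has a price. Knowing the arm may change diet, exercise and engagement, and the participant may reveal it to staff who are meant to stay blinded.

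These arguments limit the size of the problem. They do not remove its source: the rule says study, no follow-up is provided, and the analysis relies on missing at random with nothing planned to test it.

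**Conclusion.** The point holds as a modest and avoidable design weakness. The withdrawal rule loses outcomes that the stated ITT principle calls for, and the analysis replaces them under an assumption that is doubtful for participants who leave after a safety event.

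The overstatement is at most 0.05 kg per active-arm case before month 3, about 7% of the 0.67 kg standard error. Two cases give at most 0.10 kg and four at most 0.20 kg, with half of each if half the effect is lost. These bounds assume a 2 kg effect, 40 per arm, imputation within arm, and an off-drug weight no worse than placebo. They are not forecasts. If unblinding is rare, the effect on the primary endpoint is small.

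The documents do not support a claim that the primary result would be materially biased toward the drug. That would need several active-arm unblindings within three months, and nothing in the text gives such a rate. The change is still worth making, because weights not collected cannot be recovered at analysis.

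**What to change.** In Randomization and Allocation, separate unblinding from leaving the study. After unblinding, and with consent, ask the participant to attend the remaining scheduled clinic visits for weight. In Statistical Analysis, include those weights as randomized and record the unblinding as an intercurrent event. For participants who decline, a sensitivity analysis that does not assume missing at random would show how much the result depends on the imputation. The rules on when to unblind and when to stop treatment stay as the protocol sets them.

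The planned sample size and alpha do not change. The cost is a short wording change and a few participant visits that the schedule already contains; the documents include no budget, so that cost cannot be put in money. A participant who knows their arm could change behaviour or disclose it to blinded staff. They should be asked not to disclose it, and the record of unblinding lets the analysis identify their data.

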Along with the prescription for a reduced calorie diet, a comprehensive lifestyle intervention program should prescribe increased aerobic physical activity (such as brisk walking) for ≥150 min/week (equal to ≥30 min/d most days of the week), and a goal of >10,000 steps per day. Higher levels of physical activity, approximately 200 to 300 min/wk., are recommended to maintain the weight lost or minimize weight regain in the long term (>1 year)¹¹. The diet and physical activity can be in combination with a hospital/university or commercial behavior program; these are comprehensive

lifestyle interventions that usually provide structured behavior strategies to facilitate adherence to diet and activity recommendations. These strategies include regular self-monitoring of food intake, body weight, physical activity, and food cravings. These same behaviors are recommended to maintain lost weight, with the addition of frequent (i.e., weekly or more frequent) monitoring of body weight¹².

Pharmacotherapy

In addition to diet, exercise and behavioral modification, pharmacotherapies should be considered as an adjunct to lifestyle changes in patients who have been unable to lose and maintain weight with diet and exercise alone. They should also be considered in people whose history or clinical circumstances require expedited weight loss. Medication should not be used alone, but in combination with an intensive lifestyle program.

Pharmacotherapy for the treatment of obesity can be considered if a patient has a body mass index (BMI) $\geq 30 \text{ kg/m}^2$ or a BMI $\geq 27 \text{ kg/m}^2$ with weight-related co-morbidities such as hypertension, type 2 diabetes, dyslipidemia and obstructive sleep apnea¹². Medical therapy should be initiated with dose escalation based on efficacy and tolerability to the recommended dose. An assessment of efficacy and safety at least monthly for the first three months and then at least every three months. In patients who have cardiovascular disease, guidelines recommend against prescribing sympathomimetic agents such as phentermine and phentermine/topiramate extended release (ER). Lorcaserin and orlistat are safer alternatives. In patients with T2DM, the guidelines suggest antidiabetic agents that promote weight loss such as glucagon-like peptide (GLP-1) analogs which reduce hyperglycemia in addition to the first-line agent for T2DM, metformin¹³.

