Medication / dose	Clinical data	Mean weight change from baseline after 1 year	Weight loss after 1 year (Proportion of participants)			References
			>5%	>10%	>15%	
Orlistat 120 mg TID	Clinical data from three trials	-6.0 to 10.3 Kg vs -2.6 to 6.1 Kg with placebo	36–67% (vs. 16–43.6%)	17 - 38.9 (vs. 8.8 – 24.8)	NA	¹⁴⁻¹⁶
Phentermine/ topiramate ER 15 mg/92 mg QD	1-year trial, people with obesity (BMI $\geq 35 \text{ kg/m}^2$)	-10.9% vs -1.6% with placebo	70% (vs. 21%)	48% (vs. 7%)	NA	¹⁷
Lorcaserin 10 mg BID	2-year trial, people with obesity or overweight and ≥ 1 comorbidity	-5.8% vs -2.5% with placebo	47% (vs. 23%)	22.6 (vs. 7.7)	NA	¹⁸
Naltrexone/ bupropion SR 32 mg/360 mg	Four 56-week trials, people with obesity and ≥ 1 comorbidity	-5.4% vs -1.3% with placebo (COR-I)	42% (vs. 17%)	28.3 (vs. 5.7)	13.5 (vs. 2.4)	¹⁹
Liraglutide 3.0 mg QD	56-week trial, people with obesity or overweight and ≥ 1 comorbidity	-7.4% vs -3.0% with placebo	62% (vs. 34%)	33.1% (vs. 10.6%)	14.4% (vs. 3.5%)	²⁰

Phentermine-Topiramate Extended Release: When low-dose, controlled-release, phentermine was combined with the glutamatergic and GABA-ergic antiepileptic topiramate in a large phase III study (more than 1400 participants on treatment arms with different doses), subjects lost 10.2 kg on 15/92 mg combination therapy vs. 1.4 kg on placebo over 56 weeks ¹⁷. The most common adverse events were dry mouth, paresthesias, constipation, insomnia, dizziness, and dysgeusia. Depression- and anxiety-related adverse events were also observed. The medication had favorable effects on glycemia, including prevent progression to diabetes, improvements in lipids, blood pressure, sleep apnea, and quality of life measures. There was also, as previously noted, a small but consistent increase in pulse rate ²¹. The overall rate of adverse effects decreased in weeks 56–108 compared to weeks 0–56; among which dry mouth, constipation and paresthesias were the most prevalent. There were 19 pregnancies carried to term during these studies none of which resulted in congenital abnormalities ^{21–23}.

[figure not shown]

Figure 1. Effects of phentermine plus topiramate on bodyweight. Patients with at least 5% and at least 10% weight loss. ¹

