In July 2012, the FDA voted for approval of phentermine (3.75–15mg/d) plus extended release topiramate (23–92mg/d) as an adjunct to diet and physical activity for treatment of obesity among adult individuals with $\text{BMI} \geq 30 \text{ kg/m}^2$ or $\text{BMI} \geq 27 \text{ kg/m}^2$ with at least one obesity-related comorbid condition. The drug will carry a warning of potential increased risk for orofacial clefts in neonates exposed to topiramate during the first trimester of gestation and will be subject to a Risk Evaluation and Mitigation Strategy (REMS) that will restrict prescribing to trained clinicians, will require effective contraception and monthly pregnancy tests for reproductive age women, and will restrict dispensing to specific mail-order pharmacies. The company is also required to carry a long-term cardiovascular outcomes trial. No randomized pediatric studies have as yet been reported. Noteworthy, the high dose of PhenTop was associated with a mean weight loss of 9.8%; however, only 48% of patients lost >10% of their body weight, and 30% of patients lost <5% of their body weight (Figure 1).

Wearable Activity Trackers

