- e) Subject must have an Apple iPhone 6s or later with iOS 13 or later and be willing to download the VitalCare (VitalTech Affiliates LLC) application from the Apple App Store.
- f) Able to provide written informed consent prior to any study procedures, and be willing and able to comply with study procedures

Exclusion criteria

- a) History of Abdominal bariatric surgery
- b) Weight is greater than 450 lbs (204 kg)
- c) Recent use (within the last three months) of any antiobesity medication
- d) Recent weight change (gain or loss weight greater than 3% TBW in the last 3 months)
- e) Positive history of chronic gastrointestinal diseases, or systemic disease that could affect gastrointestinal motility, or use of medications that may alter gastrointestinal motility, appetite or absorption, e.g., orlistat, within the last 6 months.

- f) Significant untreated psychiatric dysfunction based upon screening with the Hospital Anxiety and Depression Inventory (HAD), and the Questionnaire on Eating and Weight Patterns (binge eating disorders and bulimia). If such a dysfunction is identified by an anxiety or depression score >11 or difficulties with substance or eating disorders, the participant will be excluded and given a referral letter to his/her primary care doctor for further appraisal and follow-up.
- g) Hypersensitivity or contraindication to the study medication.
- h) Participant unable or unwilling to follow protocol including use of the wearable activity tracker, digital wellness devices, VitalCare application, or unwilling to sign consent.
- i) Principal Investigator discretion

Anthropometrics and Metabolic Characteristics studies

Anthropometrics Measurements: will be taken of height, weight, blood pressure, pulse, waist and hip ratio, respiration rate and temperature at screening, baseline, randomization day and visit 5, 6, 7, 8 and 9.

Baseline Characteristic studies:

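### No entry criterion clearly requires excluding people with cardiovascular disease, although the protocol's own background reports guideline advice against the study drug in that group

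*Combined protocol and SAP*

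**What the plan says.** **The restriction.** The Pharmacotherapy section of the Introduction states: "In patients who have cardiovascular disease, guidelines recommend against prescribing sympathomimetic agents such as phentermine and phentermine/topiramate extended release (ER"). The next sentence reads: "Lorcaserin and orlistat are safer alternatives". The section on phentermine-topiramate ER reports "a small but consistent increase in pulse rate" and, in its account of the approval, adds: "The company is also required to carry a long-term cardiovascular outcomes trial".

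**The entry criteria (Selection Participants).** Inclusion a qualifies the population: "these will be otherwise healthy individuals with no unstable psychiatric disease and controlled comorbidities or other diseases". Exclusion g reads "Hypersensitivity or contraindication to the study medication" and lists no condition. The Medication section refers the reader to the FDA drug information package. Exclusion i is the discretion of the principal investigator. None of inclusion a to f or exclusion a to i mentions cardiovascular disease. The age range is 18 to 75 years.

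**How another drug-specific restriction is handled.** The same account of the approval says that the risk program "will require effective contraception and monthly pregnancy tests for reproductive age women". Eligibility carries this over. Inclusion c requires a negative pregnancy test, and inclusion d states: "Women of childbearing potential must agree to use a method of effective contraception during study participation".

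**The concern.** The protocol singles out a group for whom it says the study drug is advised against and other drugs are safer. It then does not clearly turn that statement into an entry rule. Each criterion that might do so is general and leaves room for interpretation. A screening physician could in good faith enroll someone with stable, treated cardiovascular disease, and another could in good faith refuse the same person.

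What is at stake is participant safety and consistent screening, not inference. Randomization is 1:1, so a person enrolled this way has a 1 in 2 chance of being assigned the active drug for up to 12 months, rising after 15 days to 7.5/46 mg daily.

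**Working it through.** The plan gives no figure on this point to reproduce. The check sets the restriction beside each criterion, and then shows a labelled range for the number of people involved.

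**Step 1. Does any criterion require exclusion?**

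| Criterion | What it does for stable, treated cardiovascular disease |
|---|---|
| Inclusion a | Two signals. The demand for otherwise healthy people points toward exclusion. The allowance for controlled comorbidities or other diseases points toward admission. |
| Inclusion b to f | Age, sex and pregnancy testing, contraception, phone, consent. Not relevant. |
| Exclusion a to f, and h | Bariatric surgery, weight limit, recent drugs, weight change, gastrointestinal and psychiatric conditions, unwillingness. These would catch such a person only incidentally. |
| Exclusion g | Applies only if cardiovascular disease counts as a contraindication. The background reports a recommendation against use, which is not the same term, and the protocol lists no contraindications. |
| Exclusion i | Permits exclusion but does not require it. |

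**Step 2. How should inclusion a be read?** Otherwise healthy cannot mean free of all disease. The secondary endpoints cover diabetes, hypertension, hyperlipidemia, sleep apnea and joint disease, so people with those conditions are meant to enter. The most natural reading of the allowance is that it refers to these obesity-related conditions. However, the wording also extends to other diseases that are controlled, and nothing in the sentence draws the line before cardiovascular disease.

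**Step 3. Two cases for exclusion g.**
- If the package lists cardiovascular disease as a contraindication, g already excludes it, and a new criterion only restates this.
- If it does not, a person with stable, treated disease can be read as meeting inclusion a and need not meet any of exclusions a to h. Only the stricter reading of a, or discretion under i, keeps that person out.

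The documents do not show which case holds. The protocol's summary of the approval mentions an orofacial-cleft warning, the pregnancy measures and an outcomes trial. It is a short background paragraph, so its silence on a cardiovascular contraindication settles nothing.

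**Step 4. How many people?** The documents give no rate of cardiovascular disease among those enrolled, so the rate p is an assumption. With 80 participants randomized 1:1, the number enrolled is 80 × p and the expected number on active drug is 80 × p × 0.5.

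| Assumed p | Enrolled | Expected on active drug |
|---|---|---|
| 0 | 0 | 0 |
| 0.025 | 2 | 1 |
| 0.05 | 4 | 2 |
| 0.10 | 8 | 4 |

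**Step 5. Effect on the statistics.** The sample-size inputs (SD 3 kg, difference 2 kg, 37 per group) and the final two-sided level of 0.0492 do not depend on this criterion. Nothing in the primary analysis changes.

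**The case against.** The strongest reply is that the plan already covers these patients. Inclusion a asks for otherwise healthy people, and someone with established cardiovascular disease does not fit that description comfortably. Exclusion g may cover them outright. A history and physical examination take place at Visit 1, and discretion is available under i. Nothing in the documents suggests that such patients would in fact be enrolled. All of this stands. It limits the point to a gap in explicit wording and keeps the possible number at zero or above.

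It does not remove the point. Exclusions e and f show that the protocol is willing to name conditions, and f even gives a score cutoff. The pregnancy restriction is also written into eligibility. That comparison has limits: it is found in inclusion c and d rather than in g, it follows from a formal risk program, and pregnancy can arise during the trial, which explains the repeat testing. What remains is that one stated drug restriction became an entry rule and the other did not.

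A reader might go further in three ways that the documents do not support.
- *That the trial breaches a contraindication.* The background reports a recommendation, and the package is not available here.
- *That safety monitoring is inadequate.* The Pharmacotherapy section calls for assessment of efficacy and safety at least monthly for three months and then at least every three months. The visit table schedules adverse-event assessment at all 13 contacts after randomization, and vital signs at weeks 2 and 4 and months 3, 6, 9 and 12. From month 3 on, even the vital signs alone meet the three-monthly interval. The Randomization and Allocation section also provides for safety unblinding with withdrawal.
- *That the pulse effect is large.* The protocol calls it small, reports favorable effects on blood pressure in the same paragraph, and does not tie the pulse change to the 7.5/46 mg dose used here.

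**Conclusion.** The point holds as a gap in eligibility wording. The protocol reports advice against its own study drug in a named group, and no criterion clearly requires that this group be excluded. The gap is real only if the drug information package does not list cardiovascular disease as a contraindication, which cannot be settled from the documents. Its size is unknown and may be zero. The range of 0 to 8 enrolled and 0 to 4 expected on active drug rests entirely on assumed rates of 0% to 10%. Investigators can already exclude these patients. There is no effect on the primary comparison, power or significance level. The change is worth considering because it is inexpensive and makes screening consistent; it is not a condition for the validity of the trial.

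**What to change.** Add a separate exclusion criterion that depends neither on the word contraindication nor on the drug package. For example: *Known cardiovascular disease (for example coronary artery disease, stroke, heart failure or clinically significant arrhythmia), other than controlled hypertension or dyslipidemia.*

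The investigators should fix the list of diagnoses before enrollment and assess it from the medical history and physical examination already scheduled at Visit 1. A separate line is better than an addition to g. If the package does not list the disease, an addition to g would call it a contraindication that the package does not recognize, and the package would give no diagnoses to work from.

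The exception for controlled hypertension and dyslipidemia keeps the participants who inform the blood-pressure and lipid endpoints. It also fits the Pharmacotherapy section, which counts both among the comorbidities that support drug treatment.

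The cost is one line of text, possibly a few more screen failures and slightly narrower generalizability. No visit, test or sample size changes.
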